5.1.2 Tablet Formulation Introduction, Evaluation, and SMC Decision Making

In addition to the capsule formulation used in this and previous studies, a tablet formulation has been developed. Owing to its formulation characteristics, dissolution of the drug substance may be enhanced in the tablet compared to the capsule formulation. CCI

Physiology-based (GastroPlus) modeling of the human absorption which is predicted to be > 90% at daily doses up to 400 mg, and > 50% at daily doses up to 1000 mg. To take a conservative approach, exposure increases of 2-fold relative to the capsule formulation is assumed.

Currently doses and exposures of up to 200 mg QD of the capsule formulation in combination with RT are considered safe and well tolerated by the SMC. Dose escalation in the current trial is ongoing and the dose of 300 mg is currently being tested. Considering the scenario of an exposure increase of 2-fold of the tablet relative to the capsule formulation a starting dose of 100 mg QD has been selected.

Introduction of the tablet in the Phase Ia part of Arm A

The tablet formulation will be introduced in Phase Ia Arm A of this trial taking into account the available clinical experience and exposure reached after administration of the capsule formulation of M3814 in combination with RT. Subjects will receive the tablet formulation at a starting dose of 100 mg QD on trial days FD 1-5 and FD 7-10. On trial day FD 6, the current capsule formulation will be given as a single dose of 100 mg to allow an intra-individual cross over comparison of single dose PK between the tablet and the capsule formulation. The administration of M3814 formulations will take place 1.5 hours (\pm 30 minutes) before the start of RT. In subsequent dose levels tablet and capsule formulations will always be given using the same dose.

After an initial cohort of 3 patients has been treated at the initial tablet dose of 100 mg, the SMC will decide to treat further patients at this tablet dose with the same dose, or to test optional dose levels (either decreases or increases of dose, the nominal dose will be the same as for the tablets). To decide on the doses to be tested, the SMC will review all available safety, tolerability and PK data, e.g., t_{max} , C_{max} , AUC_{0-24} after single doses of the capsule (FD6) and the tablet (FD1) formulations. The goal is to achieve exposures close to those achieved at the RP2D established for the capsule.

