After review of the safety, tolerability, and PK data from this cohort in relation to the data obtained in the ongoing dose escalation, the SMC may decide to test further tablet dose levels. The aim is to confirm the RP2D that has been defined for the capsule, using the tablet formulation.

The design of the tablet testing cohorts in the Phase Ia part of Arm A also includes intra-individual comparison of single dose PK of M3814 after administration of the tablet versus capsule. The capsule administered on FD6 after a 48-hour wash-out is not expected to be influenced by the previous administration of M3814 tablets on FD1 to FD5, considering the median terminal half-life of 5.5 hours (range 2.0 to 8.8 hours, preliminary data estimated in the **CCI** [REDACTED]) after multiple daily dosing. Clinical safety, tolerability, and PK results obtained in Phase Ia Arm A will determine subsequent introduction of the tablet in other parts of the trial.

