6.2 Final Analysis

Cut-off date:

All final, planned analyses identified in the Clinical Trial Protocol and in this IAP will be performed only after the last subject has completed one year of follow-up, all data queries resolved, and the database locked.

A data review meeting will be held prior to database lock. In addition, no database can be locked until this IAP has been approved.

7

Changes to the Planned Analyses in the Clinical Trial Protocol

The protocol specifies the following PK parameters to be reported for Fraction Day 10: CLss/f, Vss/f, AUC_{0-t}, and AUC_t. These will not be calculated or reported due to the limited number of PK samples to be collected in the terminal phase leading to unreliable parameter estimates, please refer to Section 16.1 for a complete list of PK parameters which will be reported. In addition, standard error of the mean will not be a descriptive statistic used to describe PK variables.

In section 8.5.4.3 of the protocol the following analysis is described regarding data coming from the physical examination: "Data will be further analyzed using concentration effect modeling for baseline-corrected QTcF values obtained at Day 1." This analysis will not be performed so will not be included in this analysis plan.

In the protocol a number of biomarker analysis sets are defined. These will not be used and instead the SAF analysis set will be used for biomarker analyses.

7.1

COVID-19 Impact

Additional listings will be generated to assess potential impacts of COVID-19 to this study including:

- listing of participants potentially affected by pandemic and with any AEs or PDs related to COVID-19
- listing of PDs related to COVID-19
- listing of AEs related to COVID-19.

8

Protocol Deviations and Analysis Sets

8.1

Definition of Protocol Deviations and Analysis Sets

Important protocol deviations are protocol deviations that might significantly affect the completeness, accuracy, and/or reliability of the study data or that might significantly affect a subject's rights, safety, or well-being.

Important protocol deviations will be categorized in to one of the following:

- Subject enrolled and dosed on the study who did not satisfy enrolment criteria
- Subject fulfills withdrawal criteria whilst on the study but is not withdrawn
- Subject is administered the wrong treatment or an incorrect dose
- Subject is administered or takes concomitant medication excluded by the CTP

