16.1 Pharmacokinetics

Population: PK analysis set

Non-compartmental computation of PK parameters will be performed using the computer program Phoenix® WinNonlin® version 6.4, or higher (Pharsight Corporation, a Certara Company, Princeton, New Jersey). The statistical software SAS® (Statistical Analysis System, SAS-Institute, Cary North Carolina), Windows version 9.2 or higher will be used to produce tables, listings and figures. Figures will be prepared with SAS Version 9.2, or higher.

Pharmacokinetic parameters will be calculated using standard non-compartmental methods and the actual administered dose.

For each subject with PK data, the following PK parameters will be calculated for M3814 and **CCI** as either single or multiple dose, as follows and as appropriate.

- FD1 – single dose
- **CCI** – single dose if it occurs on a Monday
- All other fraction days - multiple dose.

C_{max} Maximum observed concentration

$C_{max}/Dose$ The Dose-normalized maximum observed concentration. Normalized using the actual dose, and the formula $C_{max}/Dose$.

AUC_{0-4} Area under the concentration-time curve (AUC) from time zero to time 4 hours postdose. AUC_{0-4} will be based on the estimated concentration at 4 hours and not the concentration at the actual observation time. For **CCI** in case no regression is available and a sample has been collected at 4 hours within the protocol-defined collection window (3.5 to 4.5 hours), actual time may be used.

$AUC_{0-4}/Dose$ The Dose-normalized AUC from time zero to 4 hours postdose. Normalized using the actual dose, using the formula $AUC_{0-4}/Dose$.

AUC_{0-6} Area under the concentration-time curve (AUC) from time zero to time 6 hours postdose. AUC_{0-6} will be based on the estimated concentration at 6 hours and not the concentration at the actual observation time. In case no regression is available and a sample has been collected at 6 hours within the protocol-defined collection window (5.5 to 6.5 hours), actual time may be used.

$AUC_{0-6}/Dose$ The Dose-normalized AUC from time zero to 6 hours postdose. Normalized using the actual dose, using the formula $AUC_{0-6}/Dose$.

AUC ₀₋₁₂	Area under the concentration-time curve (AUC) from time zero to time 12 hours postdose. AUC ₀₋₁₂ will be based on the estimated concentration at 12 hours based on the elimination rate constant.

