The trough concentrations (C_{trough}) for FD2, **CCI** FD7, and **CCI** will be listed and summarized by group (e.g. dose level, fraction day, analyte), using standard descriptive statistics. Individual C_{trough} values will be plotted against actual time points on a linear scale, for all subjects by dose level. Arithmetic mean $C_{trough} \pm SD$ will also be plotted by dose level, on a linear scale.

The calculation of the AUC will be performed using the mixed log-linear trapezoidal method. The actual time of blood sampling will be used for PK parameter calculation. In cases where the actual sampling time is missing, calculations will be performed using the scheduled time.

Partial areas AUC_{0-4} AUC_{0-6} , AUC_{0-12} , and AUC_{0-24} should be calculated using the scheduled dosing interval. The actual interval calculated from CRF time data should not be used.

Pre-dose samples will be considered as if they had been taken simultaneously with the administration, and will be assigned a time of 0 hours. Concentrations below the lower limit of quantification (LLOQ), will be taken as zero for summary statistics of PK concentration data, NCA and for graphical presentations.

The regression analysis should contain data from at least 3 different time points in the terminal phase consistent with the assessment of a straight line on the log-transformed scale. Phoenix WinNonlin “best fit” methodology will be used as standard. However, in some cases, further adjustment may be made by the pharmacokineticist, if warranted, after agreement with the Sponsor. The last quantifiable concentration should always be included in the regression analysis, while the concentration at t_{max} and any concentrations below LLOQ which occur after the last quantifiable data point should not be used.

[figure not shown]
AUC_{extra} should not be greater than 20%, the coefficient of correlation (R^2) should be ≥ 0.8000 and the observation period over which the regression line is estimated should be at least twofold the resulting $t_{1/2}$ itself. If these criteria are not met, then the rate constants and all derived parameters (e.g. CL/f , and Vz/f etc.) will be included in the parameter outputs and descriptive statistics but will be flagged and discussed appropriately. Any flags will be included in the study specific SDTM/ADaM.

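### SAP 16.1 summarises terminal-slope PK values that miss its own reliability limits, cannot meet the window limit on FD10 from observed samples at nominal times, and defines no interval for the tablet/capsule ratio

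*SAP*

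**What the plan says.** **Limits and their consequence (SAP 16.1).** "The regression analysis should contain data from at least 3 different time points in the terminal phase", and the concentration at tmax is not used. The extrapolated share of AUC "should not be greater than 20%, the coefficient of correlation" (R²) should be at least 0.80, and "the observation period over which the regression line is estimated should be at least twofold the resulting" half-life. If these are not met, the rate constants and everything derived from them "will be included in the parameter outputs and descriptive statistics but will be flagged and discussed appropriately".

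**What depends on the slope (SAP 16.1).** AUC0-12 "will be based on the estimated concentration at 12 hours based on the elimination rate constant", with no fallback. AUC0-6 falls back on a sample taken at 5.5 to 6.5 h. Half-life has no day restriction. Accumulation ratios are planned for Cmax, AUC0-4, AUC0-6, AUC0-12 and AUC0-24. AUC0-24 is to be calculated on FD1, FD6 (tablet group) and FD10. On one redacted multiple-dose day, the predose value is copied forward as the 24 h value so that AUC0-24 can be computed.

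**What has been dropped (SAP section 7).** On FD10, CLss/f, Vss/f, AUC0-t and the dosing-interval AUC (AUCtau) are not reported, "due to the limited number of PK samples to be collected in the terminal phase leading to unreliable parameter estimates".

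**Sampling (protocol Table 9).** As printed, FD10 has predose, 0.5, 1, 2 and 4 h. FD1 and tablet-cohort FD6 go to 6 h, and the next day's predose serves as the 24 h value.

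**Tablet/capsule ratio.** SAP 16.1 defines Frel for Cmax, AUC0-4 and AUC0-24. In SAP section 9 the list of PK-parameter statistics contains no confidence interval, while the rounding rule for the same statistics mentions a 95% CI. Protocol 5.1.2 explains the purpose of the tablet cohorts: "The goal is to achieve exposures close to those achieved at the RP2D established for the capsule".

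**The concern.** A limit that does not change the summary protects only the reader of the listings. Cohorts have 3 subjects, so one poor slope carries a third of the weight in a mean and can dominate a geometric CV. FD10 is where this bites: sampling stops early relative to the half-life, yet half-life, AUC0-6, AUC0-12 and their accumulation ratios are still reported there. The two SAP sections also disagree. Section 7 drops AUCtau on FD10 as unreliable, while 16.1 keeps AUC0-24; under once-daily dosing both cover the same 24 h.

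The second issue is separate. The single-dose comparison of tablet with capsule supports the choice of tablet doses (protocol 6.3.1), from dose levels of up to 6 subjects (protocol 5.1.2). A ratio reported from so few subjects without an interval invites over-reading.

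**Working it through.** The documents give no planned precision for these analyses, so there is no figure to reproduce.

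**1. Window needed.** Protocol 5.2 gives a "median terminal half-life of 5.5 hours (range 2.0 to 8.8 hours", preliminary). Twice the half-life:
- 2 × 2.0 = 4.0 h
- 2 × 5.5 = 11.0 h
- 2 × 8.8 = 17.6 h

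**2. Window available (nominal times, points after tmax, at least 3 required).**

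| Day and data | tmax | Points | Window | Longest half-life that passes |
|---|---|---|---|---|
| FD10, observed | 0.5 h | 1, 2, 4 h | 3 h | 1.5 h |
| FD10, observed | 1 h or later | 2 or fewer | none | no lambda-z |
| FD10 + duplicated predose at 24 h | 0.5 or 1 h | 3 or 4 points to 24 h | 22–23 h | at least 11.0 h |
| FD10 + duplicated predose at 24 h | 2 h | 4, 24 h | none | no lambda-z |
| FD1/FD6 + next-day predose | up to 2 h | 3 to 5 points to 24 h | 20–23 h | at least 10.0 h |
| FD1/FD6, 24 h sample missing | 0.5 or 1 h | 3 or 4 points to 6 h | 4–5 h | 2.0–2.5 h |

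On observed FD10 samples, a fit exists only with tmax at 0.5 h, and it passes only for half-lives up to 1.5 h, below the whole stated range. At the extremes of the permitted sampling windows (1 h sample at 0.5 h, 4 h sample at 4.5 h) the span is 4.0 h, which just reaches the limit at a half-life of 2.0 h and no further.

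**3. Extrapolated AUC on FD1/FD6.** A one-compartment oral model with assumed ka of 0.8 to 3.0 per h, with the 24 h sample, gives about 0%, 5–6% and 15.5–17% at half-lives of 2.0, 5.5 and 8.8 h. All are within 20%. Without the 24 h sample it is 49–56% at 5.5 h.

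**4. How much of FD10 AUC0-12 lies after the last sample.** Mono-exponential approximation, k = ln 2 / half-life, share = (e^(−4k) − e^(−12k)) / (1 − e^(−12k)):
- 2.0 h: (0.250 − 0.016) / 0.984 = 24%
- 5.5 h: (0.604 − 0.220) / 0.780 = 49%
- 8.8 h: (0.730 − 0.389) / 0.611 = 56%

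This is the part that rests on the slope. It is not the error made by keeping flagged values.

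**5. Precision of Frel.** The within-subject CV is not in the documents, so it is assumed. SD of the log ratio = sqrt(2 ln(1 + CV²)); CI factor = exp(t × SD / sqrt(n)), with n − 1 degrees of freedom.
- CV 30%: SD = sqrt(2 ln 1.09) = 0.415
- 90% CI, n = 3: exp(2.920 × 0.415 / 1.732) = 2.01
- 90% CI, n = 6: exp(2.015 × 0.415 / 2.449) = 1.41
- 90% CI, n = 12 (for example, two full dose levels pooled): 1.24

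Protocol 5.1.2 assumes a 2-fold exposure increase. For an observed ratio of 2.0 with n = 6, the 95% CI is 1.49–2.68 at CV 20%, 1.29–3.09 at 30%, 1.13–3.54 at 40% and 0.99–4.03 at 50%.

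**The case against.** Several counter-arguments stand.

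- **Failing values are not shown to be routine on FD10.** A reader might infer that 4 h sampling fills the FD10 tables with bad slopes. The documents do not support that. With tmax at 1 h or later, observed samples give no slope, so there is nothing to retain. CL/f, Vz/f and AUC0-∞ are confined to FD1 and a tablet-group day, and section 7 already removed the FD10 clearance and volume terms. The defect on FD10 is a mix of missing values, some unreliable ones, and silence about the duplicated predose.
- **Flag-and-keep is prespecified and disclosed.** The limits are worded as what should hold, and extrapolated AUC, regression interval, number of points and adjusted R² are listed for each subject. This is fair, but a flag in a listing does not alter a summary table.
- **Excluding failures has its own bias.** The window and extrapolation limits fail preferentially in subjects with long half-lives, so dropping them would pull half-life and AUC summaries down. This stands, and it is why both versions are proposed rather than exclusion.
- **An interval is not plainly absent.** The rounding rule in SAP section 9 mentions a 95% CI, and one could be rebuilt from n, geometric mean and geometric CV. What stands is that the list and the rounding rule disagree and that no scale or method is named for Frel. Frel for Cmax and AUC0-4 needs little or no extrapolation; only Frel for AUC0-24 may inherit a poor slope.
- **The link to dose decisions.** A reader might infer that the SMC chooses tablet doses from this SAP's table. SAP section 4 places SMC analyses in a separate plan that was not supplied, and protocol 5.1.2 has the SMC weigh all safety, tolerability and PK data. Protocol 8.5.3.1.1 calls the PK tests exploratory.

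**Conclusion.** The point holds as a low-cost improvement to the trial report. Slope-derived values that miss the SAP's limits enter the descriptive statistics with no alternative summary. On FD10, observed samples at nominal times give at most a 3 h window against the 4.0 to 17.6 h needed, so half-life, AUC0-6, AUC0-12 and their accumulation ratios are missing or unreliable unless the duplicated predose may enter the regression, which the SAP leaves open. Between about a quarter and just over half of FD10 AUC0-12 rests on that slope. FD1 and FD6 can meet the limits when the next-day predose is available and tmax is 2 h or earlier. Dropping AUCtau while keeping AUC0-24 on FD10 is an unexplained inconsistency. Frel has no defined interval method, and with 3 to 6 subjects its uncertainty is large.

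This rests on Table 9 as printed, on reading redacted day labels in SAP 16.1 as FD6 and FD10, on a preliminary half-life range, and on assumed values for ka and within-subject CV. It does not show that any SMC decision was made on these tables.

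**What to change.** 1. In SAP 16.1, present each lambda-z-derived summary twice: with all values and without flagged ones, giving n for each.
2. For FD10, base accumulation on Cmax and AUC0-4, and list half-life, AUC0-6 and AUC0-12 without summarising them. State whether the duplicated predose may enter the lambda-z regression. Explain why AUC0-24 is kept when AUCtau is dropped, or treat the two alike.
3. Estimate Frel for Cmax, AUC0-4 and AUC0-24 with one paired log-scale model (FD1 tablet against FD6 capsule), pooled across tablet dose levels, and report the geometric mean ratio with its 90% CI. Show the ratio by dose level alongside, because pooling assumes that it is constant over dose. Note that the order is fixed, so the interval does not cover any day effect. Align the statistics list and the rounding rule in SAP section 9.

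The cost is SAP wording, some extra summary columns and one short model on data already collected.

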5.1.1 Dose Escalation Rules

The criteria for dose escalation are based on the occurrence of AEs and/or DLTs that are unrelated to underlying conditions and/or to concomitant medication during the DLT period in evaluable subjects in each cohort. The DLT window of 5 weeks (Phase Ia, Arm A) or 12 weeks (Phase Ia, Arm B and the first 3 subjects in the expansion cohort for Arm A [NSCLC]) after the start of M3814 treatment allows an evaluation of acute toxicity. M3814 dose escalation will not proceed to the next dose level until all subjects in the previous dose level have been observed for the duration of the DLT period. However, RT/CRT and the combination of RT/CRT and M3814 can also give rise to later toxicities. A 3-month mid-term safety follow-up will be performed in all subjects in the Phase Ia part of the trial and, once available, these data will also guide subsequent dose escalation and the establishment of the RP2D. Available PK and PD data will also be taken into consideration.

Dose Escalation During Phase Ia

A Bayesian two-parameter logistic regression model with overdose control will be used to assist the SMC with dose selection during the Phase Ia dose escalation (capsule formulation in Arm A/B, and tablet formulation in Arm B). Cohorts of 3 subjects each will be treated at the same dose level (capsule starting dose: 100 mg QD for Arm A and 50 mg QD for Arm B). The model incorporates prior information (from nonclinical data) and observed information from each completed cohort (and data from all previous cohorts) to provide a recommended dose for the next cohort. A preselected set of acceptable doses are considered by the model, however doses which are not part of the prespecified set may be chosen as well. The model ensures that recommended doses correspond to a probability of less than 25% that the true DLT rate is more than 35% in Arm A and 45% in Arm B. Dose escalation will stop in each arm as soon as the first of the following stopping rules apply: a maximum of 30 subjects are included, more than three cohorts are assigned to the same dose level, or the estimate of DLT probability at the MTD reaches a sufficient precision (see Section 8 for more details).

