8.5.3 Analysis of Secondary Endpoints

8.5.3.1 Pharmacokinetics

8.5.3.1.1 Descriptive Statistics

The PK variables will be analyzed descriptively for each treatment separately. Descriptive statistics include N, arithmetic mean, geometric mean, SD, standard error of the mean, median, minimum, maximum, coefficient of variation (%), and geometric coefficient of variation. The drug concentration in plasma at each sampling time will be presented on the original scale for all subjects who participate in the trial and provide at least 1 plasma concentration of M3814. Values below the lower limit of quantification will be taken as zero for descriptive statistics of concentrations.

[figure not shown]
Individual plasma concentration-time profiles (linear and semi-logarithmic scale) will be plotted by treatment. Mean plasma concentrations per treatment will be plotted with SD by scheduled time points. If evidence is obtained that weight affects the PK parameters, then analyses will also be performed for weight-normalized PK parameters. Formal statistical hypotheses are not set up. All statistical tests will be performed in an exploratory manner. All analyses will be based on the PK analysis set.

Details of the statistical analyses will be described in the SAP.

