8.5.3.1.2 Analysis of Dose Proportionality

Details of the statistical analyses will be described in the SAP.

CCI

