8.2 Definition of Analysis Sets and Subgroups

All Subjects Analysis Set (ALL):

The All subjects (ALL) analysis set will include all the subjects who have signed the ICFs (i.e., screening failures plus subjects enrolled).

Safety Analysis Set (SAF):

The Safety analysis set will include all subjects who receive at least one administration of the trial treatment (either M3814, RT or Cisplatin).

Full Analysis Set (FAS):

The Full Analysis Set will include all subjects who receive at least one administration of the trial treatment.

Dose Escalation Analysis Set (DE) :

The Dose Escalation (DE) analysis set will include all subjects treated in dose escalation cohorts who receive at least 80% of M3814 and RT planned dose and complete the DLT period (through 5 weeks [Phase Ia, Arm A] or 12 weeks [Phase Ia, Arm B] after start of M3814 treatment). The DE set will also include subjects treated in dose escalation cohorts who experience a DLT during the DLT period regardless of the received amount of each drug.

Pharmacokinetics Analysis Set (PK):

The PK evaluation (PK) analysis set in Phase Ia and Phase Ib parts will include subjects who have received at least the first dose of the drug and provided PK samples as per protocol for at least 6 hours following first dosing on Fraction Day 1.

Table 1: Summary of analyses and associated analysis set

Analyses	ALL	SAF	FAS	DE	PK
Disposition and deaths	✓				
Baseline Assessments		✓			
Past and Concomitant Therapies		✓			
Compliance and Exposure		✓			

CONFIDENTIAL
INFORMATION

12/60

Analyses	ALL	SAF	FAS	DE	PK
Primary endpoint: DLTs				✓	
Secondary efficacy endpoints			✓		
Safety and tolerability		✓			
Biomarker		✓			
Pharmacokinetics					✓

9

General Specifications for Data Analyses

Statistical analyses will be performed with SAS 9.4 or higher.

Pooling of centers:

Because of the anticipated small number of subjects enrolled in each center, data will be pooled across centers, and the factor center will not be considered in statistical models or for subgroup analyses.

Presentation of continuous and qualitative variables:

All outputs will be provided for each arm separately. No data between arms will be pooled, unless otherwise stated. For each arm, data will be presented by formulation, dose level and overall unless specified otherwise. The dose level will be defined by the planned dose of the corresponding cohort. If several cohorts have same dose level, there will be pooled together for all summary outputs.

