Continuous variables will be summarized using descriptive statistics, i.e.

- Number and percentage of subjects (n (%)), number and percentage of subjects with missing values (Missing (%))
- Mean, 95% confidence intervals, as appropriate
- Standard deviation
- Median
- Q1, and Q3
- Minimum, and maximum

If there are no missing values, this should be indicated by a 0 (0.0).

Missing statistics, e.g, when they cannot be calculated, should be presented as “nd”. For example, if n=1, the standard deviation cannot be computed and should be presented as “nd”.

Qualitative variables will be summarized by frequencies and percentages.

Unless otherwise stated, the calculation of proportions will be based on the number of subjects of the analysis set of interest. Therefore, counts of missing observations will be included in the denominator and presented as a separate category.

Presentation of PK Concentration Data

M3814 and **CCI** concentration data will be descriptively summarized using: number of non-missing observations (n), arithmetic mean (Mean), standard deviation (SD), coefficient of variation (CV%), minimum (Min), median (Median) and maximum (Max). In $n \leq 2$, only n, Min, and Max will be reported.

Descriptive statistics of PK concentration data will be calculated using values with the same precision as the source data, and rounded for reporting purposes only. The following conventions will be applied when reporting descriptive statistics of PK concentration data:

Mean, Min, Median, Max: 3 significant digits

SD: 4 significant digits

CV%: 1 decimal place

Presentation of PK Parameter Data

Pharmacokinetic parameter data will be descriptively summarized using: n, Mean, SD, CV%, Min, Median, Max, geometric mean (GeoMean), and the geometric coefficient of variation (GeoCV). For time to reach maximum observed concentration (t_{max}), only n, Min, Median, and Max will be reported.

The PK parameter maximum observed plasma concentration (C_{max}) will be reported with the same precision as the source data. All other PK parameters will be reported to 3 significant figures. In export datasets, as well as in the SDTM PP domain, PK parameters will be provided with full precision, and will not be rounded. Descriptive statistics of PK parameter data will be calculated using full precision values, and rounded for reporting purposes only.

The following conventions will be applied when reporting descriptive statistics of PK parameter data:

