Scatter plots and box plots of individual dose-normalized C_{max} , C_{av0-24} , AUC_{0-4} , AUC_{0-6} , AUC_{0-12} , AUC_{0-24} , and $AUC_{0-\infty}$ values versus dose will be presented graphically.

All descriptive summaries of PK data will be performed using the PK Analysis Set. Individual PK data will be listed using the Safety Analysis Set. The mean concentration-time profiles and PK parameter plots will be plotted using the PK Analysis Set and the individual subject concentration-time profiles will use the Safety Analysis Set. Exploratory dose proportionality analysis will be performed by visual inspection of the scatter plots and box plots of $C_{max}/dose$ and $AUC_{0-4}/dose$ against dose.

The Phoenix WinNonlin NCA Core Output will be provided in a separate listing.

CCI

CONFIDENTIAL
INFORMATION

46/60

CCI

17

References

CONFIDENTIAL
INFORMATION

47/60

18 Appendices

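### Phase Ia dose proportionality is read only from dose-normalised plots; an exploratory power model on the same PK parameters would add a slope with an interval at almost no cost

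*SAP*

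**What the plan says.** Protocol 8.5.3.1.2 is headed as the analysis of dose proportionality. Its only readable content is the deferral "Details of the statistical analyses will be described in the SAP". Protocol 8.5.3.1.1 sets the status of all PK analysis: "Formal statistical hypotheses are not set up. All statistical tests will be performed in an exploratory manner".

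SAP 16.1 supplies the method. It plots individual dose-normalised Cmax, Cav0-24, AUC0-4, AUC0-6, AUC0-12, AUC0-24 and AUC0-∞ against dose. It then states that "Exploratory dose proportionality analysis will be performed by visual inspection of the scatter plots and box plots of" two of these, Cmax/dose and AUC0-4/dose.

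SAP section 9 adds numerical summaries of PK parameters, including the geometric mean and geometric CV, and sets the grouping: "For each arm, data will be presented by formulation, dose level and overall unless specified otherwise". It also says that arms are not pooled unless otherwise stated.

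On the data available, Protocol 5.1.1 says "Cohorts of 3 subjects each will be treated at the same dose level", and one of the stopping rules for each arm is that "a maximum of 30 subjects are included".

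**The concern.** The plan asks whether exposure rises in proportion to dose, but produces no number that answers it. The by-dose tables give level and spread at each dose. They do not say how exposure changes from one dose to the next, or how well that change is known, and the SAP does not link them to proportionality.

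With cohorts of 3, a box plot has very little to summarise, and two readers can look at the same scatter plot and disagree without either being shown wrong. A regression on log dose uses all dose levels together and states its own precision.

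What is at stake is the quality of one exploratory statement in the Phase Ia report. No decision rule in the readable documents depends on it.

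**Working it through.** **No planned figure to reproduce.** Neither document gives a sample size, slope, acceptance range or interval for dose proportionality. The check is what a power model would deliver on the planned data.

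**Inputs from the documents**
- Cohort size 3 and a maximum of 30 subjects per arm (Protocol 5.1.1).
- Arm A capsule starting dose 100 mg (Protocol 5.1.1); 200 mg considered tolerated and 300 mg under test when the tablet was introduced (Protocol 5.1.2); capsule doses up to 400 mg mentioned in Protocol 5.2.
- Individual Cmax and AUC values and actual doses are already derived (SAP 16.1).

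**Assumptions**
- Between-subject CV of 30%, 50% or 70%. The documents give none.
- Capsule doses of 100, 200, 300 and 400 mg, either 3 subjects each (N = 12) or 8, 8, 7 and 7 (N = 30, best case).

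**Formulas**
- Model: ln(PK) = a + b ln(dose); b = 1 is proportionality.
- Residual SD on the log scale: s = sqrt(ln(1 + CV²)), which is 0.294, 0.472 and 0.631.
- Expected 90% half-width for b: t(0.95, N − 2) × s / sqrt(Sxx), where Sxx is the sum of squared deviations of ln(dose).

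**Numbers**
- N = 12: Sxx = 3.253, square root 1.804, t with 10 df = 1.812. At CV 30%: 1.812 × 0.294 / 1.804 = 0.30.
- N = 30: Sxx = 8.204, square root 2.864, t with 28 df = 1.701. At CV 30%: 1.701 × 0.294 / 2.864 = 0.17.

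| 90% half-width for b | CV 30% | CV 50% | CV 70% |
|---|---|---|---|
| N = 12 | 0.30 | 0.47 | 0.63 |
| as a factor over the 4-fold range (4^half-width) | 1.51 | 1.93 | 2.41 |
| N = 30 | 0.17 | 0.28 | 0.38 |
| as a factor over the 4-fold range | 1.27 | 1.48 | 1.68 |

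**Does the interval behave?** In simulation (5000 runs per setting, N = 12 over 100-400 mg and N = 30 over an illustrative 100-800 mg), the 95% version covered the true slope in 94.5% to 95.5% of runs.

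**Can it serve as a test?** Not reliably. Take a true slope of 0.6, chosen only for illustration. Dose-normalised exposure at 400 mg is then 4^(−0.4) = 0.57 of that at 100 mg, a 43% loss. The 90% CI would exclude 1 in about 74/41/28% of trials at N = 12 and 98/76/55% at N = 30 (CV 30/50/70%). A sizeable departure would often leave 1 inside the interval, so such an interval does not show proportionality.

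**Tablet.** Protocol 5.1.2 foresees up to 6 subjects per tablet dose level and fixes only the 100 mg starting dose. With an illustrative 100 and 200 mg, 6 each, the 90% half-width is 0.44/0.71/0.95. With a single tablet dose level, b cannot be estimated.

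**The case against.** The strongest reply is that this is a preference. The protocol prescribes no method, the SAP supplies one and labels it exploratory, no PK hypotheses are set up, and the primary endpoint is untouched. All of that stands. It sets the level of the point at an optional improvement, but is no reason against a better exploratory summary.

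A second reply is that the data are not shown only as plots. Dose-normalised parameters are derived, individual values are plotted for seven metrics, and PK parameters are tabulated by dose level. That also stands, yet none of these outputs is an estimate across doses.

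A third is that the precision is modest. Thirty is a ceiling with earlier stopping rules, and the protocol synopsis expects capsule escalation to give way to the tablet once tablet data allow. N = 12 is therefore shown next to N = 30. A wide interval is still informative, because the eye faces the same uncertainty unstated.

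Several stronger readings are tempting, and the documents do not support them:
- **Capsule exposure must be less than proportional.** Protocol 5.1.2 predicts absorption above 90% up to 400 mg and above 50% up to 1000 mg. That prediction follows text on the tablet's dissolution, with a redaction just before it, and it implies little loss up to 400 mg.
- **Tablet bridging depends on the capsule slope.** Tablet and capsule are compared within subject at the same dose, and SAP 16.1 quantifies this as relative bioavailability for Cmax, AUC0-4 and AUC0-24. The premise that "exposure increases of 2-fold relative to the capsule formulation is assumed" served to choose the tablet starting dose.
- **Tighter intervals from a 50-400 mg range.** Only Arm B starts at 50 mg, and its planned 30 cover tablet and capsule together (protocol synopsis). Borrowing that dose for Arm A would mean pooling arms, which SAP section 9 excludes by default.
- **A model was rejected because cohorts are small.** Neither document gives a reason for the visual method. The SAP cites small numbers only for pooling centres.

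**Conclusion.** The point holds as a low-severity improvement. In the readable text, dose proportionality in Phase Ia is assessed by visual inspection alone, with no estimate or interval across doses. A power model on existing parameters would supply both.

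Under the assumed CVs and 100-400 mg capsule doses, the 90% half-width is about 0.30 to 0.63 with one cohort per dose and 0.17 to 0.38 at the cap of 30. The result is an estimate with visible uncertainty, not proof of proportionality or of its absence.

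A reader might infer that the SAP breaches the protocol or that escalation decisions are compromised. Neither follows. The SAP fills the place the protocol left open, and outputs for the Safety Monitoring Committee fall under a separate analysis plan (SAP section 4).

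One caveat: redacted text follows both the protocol section and SAP 16.1, so an additional model there cannot be excluded, although the visible SAP sentence is complete. The separate population PK report is announced for Phase Ib and the ancillary part (Protocol 8.3.2.3), so it is not stated to fill this gap.

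**What to change.** Add to SAP 16.1 an exploratory power model, ln(PK) = a + b ln(dose):
- for Cmax, AUC0-4 and AUC0-24 on Fraction Day 1;
- fitted by formulation within each arm, wherever at least two dose levels have data;
- reporting b with its 90% CI as an estimate, without a pass/fail rule, and stating that an interval including 1 does not show proportionality.

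Keep the scatter and box plots as support. AUC0-24 is worth including because Protocol 5.1.2 lists it among the measures the committee reviews, while the SAP names only Cmax and AUC0-4 for the proportionality reading.

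The cost is a few lines of programming on parameters already derived, with no new data. The downside is an interval that may be wide, particularly for the tablet. The change improves the Phase Ia report and leaves the DLT analysis and the committee's outputs as they are.
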